11. QUALITY ASSURANCE PROCEDURES

The study may be monitored, or audited in accordance with the current approved protocol, GCP, relevant regulations and standard operating procedures.

12. ETHICAL AND REGULATORY CONSIDERATIONS

12.1. Declaration of Helsinki

The PI and named investigators will ensure that this study is conducted in accordance with the principles of the Declaration of Helsinki.

12.2. Guidelines for Good Clinical Practice

The PI and named investigators will ensure that this study is conducted in accordance with relevant regulations and with Good Clinical Practice.

12.3. Approvals

The protocol, informed consent form, participant information sheet and any proposed advertising material will be submitted to the Medical Sciences IDREC and host institution for written approval.

The PI and named investigators will submit and, where necessary, obtain approval from the above parties for all substantial amendments to the original approved documents.

12.4. Participant Confidentiality

The study staff will ensure that the participants' anonymity is maintained. The participants will be identified only by a participant ID number on all study documents and any electronic database, with the exception of the CRF, where participant initials may be added. All documents will be stored securely and only accessible by study staff and authorised personnel. The study will comply with the Data Protection Act, which requires data to be anonymised as soon as it is practical to do so.

[figure not shown]
Personal data may be retained after the end of the study where the participant agrees to be contacted for future studies. This information will be unlinked to the study data. For volunteers who do not wish to be contacted in the future, personally identifiable data will be shredded as soon as possible after completion of the study and within one year of completing study analyses.

12.5. Expenses and Benefits

The study investigates the potential for a therapeutic benefit of tDCS in stuttering, so participants in the study may expect an immediate direct benefit. We will explain in writing in PIS that no direct benefit can be guaranteed, and also re-iterate this verbally during the study screening process.

Participant will be reimbursed for their time and effort: PWS will get £180 for completing the study (2 x MRI, 2 x TMS; 5 x TDCS) and a control would get £40 (1xMRI + TMS). Should any participant withdraw from the study for any reason, they will be paid for their time up to that point at the rate of £10/ hour. In addition, participants who complete any screening visits but are not deemed eligible for the study will be paid £10/hour for their time and effort. Reasonable travel expenses for any visits will be reimbursed on production of receipts, or a mileage allowance provided as appropriate.

APPENDIX A: STUDY FLOW CHART

APPENDIX B: SCHEDULE OF STUDY PROCEDURES

Procedures	Visits									
	Visit 0 Day 0	Visit 1 1-2	V2 3	V3 4	V4 5	V5 6	V6 7	Visit 7 14- 15	Visit 8 +6 weeks	Visit 9 +3 months
	Screening	Baseline	Training					Follow up		
Informed consent		X								
Demographics	X	X								
Eligibility assessment	X	X								
Randomisation		X								
tDCS			X	X	X	X	X			
Speech (videoconference)	X	X						X	X	X
Speech (Live)		X	X	X	X	X	X	X		
SSI-4	X	X						X	X	X
OASES		X							X	X
MRI brain		X						X		
TMS brain		X						X		
MRI vocal tract		X						X		
Adverse event assessments		X	X	X	X	X	X	X		
BAI		X						X	X	X
PAIS		X						X	X	X
Subjective speech ratings (severity & naturalness)		X						X	X	X
Objective rating of naturalness		X	X	X	X	X	X	X	X	X

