6.5. Subsequent Visits

Visits 2-6 [Days 3-7]

These visits may take place at University testing facilities, or at the participant's home or office and will take place at the same time on each day. Participants will complete a short speech fluency assessment during reading and conversation at the start and end of the session; this assessment will be video recorded. A safety screening for tDCS will be conducted to ensure that the participant is not experiencing any discomfort/ risk, and to check that eligibility has not been compromised (for example, by use of medication). The intervention will then be delivered (sham vs. true tDCS + speech fluency training). The speech fluency training lasts approximately 40 minutes and stimulation is delivered for 20 minutes at the start of the training. Each session should last no more than one hour on each of the five days of intervention.

Visit 7 [Days 14-15]:

This visit will take place at OHBA. We will obtain behavioural measures of speech fluency, as well as complete clinical assessments (SSI-4). Following this, participants will repeat the brain and vocal tract imaging assessments (MRI and TMS) described. Standard operating procedures and safety guidelines for each of these procedures will be followed.

Visit 8 [+6 weeks following Visit 6]

This visit will be conducted via videoconference. We will obtain behavioural measures of speech fluency, as well as complete clinical assessments (SSI-4, OASES).

Visit 9 [+3 months following Visit 6]

This visit will be conducted via videoconference. We will obtain behavioural measures of speech fluency, as well as complete clinical assessments (SSI-4, OASES).

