6.7. Definition of End of Study

The end of study is the date of the last follow up (videoconference) of the last participant.

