8.2. Reporting Procedures for Serious Adverse Events

A serious adverse event (SAE) occurring to a participant will be reported to the Medical Sciences IDREC that gave a favourable opinion of the study where in the opinion of the Chief Investigator the event was 'related' (resulted from administration of any of the research procedures) and 'unexpected' in relation to those procedures. In addition, these events will be reported to the relevant safety officers at OHBA and the Department of Experimental Psychology. Reports of related and unexpected SAEs should be submitted within 15 working days of the Chief Investigator becoming aware of the event.

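### No adverse event enquiry is scheduled after Visit 7 (days 14-15), although efficacy is followed to Visit 9

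*Protocol*

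**What the plan says.** Protocol Appendix B has ten visit columns (Visits 0 to 9). The row "Adverse event assessments" carries a mark at Visits 1 to 7 and none at Visits 8 and 9. The rows for TMS, brain MRI and vocal tract MRI are marked at Visits 1 and 7. The tDCS row is marked at Visits 2 to 6.

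Protocol section 6.5 agrees. At Visit 7, after the speech and SSI-4 assessments, "participants will repeat the brain and vocal tract imaging assessments (MRI and TMS) described". Visits 8 and 9 are videoconferences, timed at six weeks and three months after Visit 6. For both, the text reads "We will obtain behavioural measures of speech fluency, as well as complete clinical assessments (SSI-4, OASES", closes the bracket there, and mentions no adverse event enquiry.

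Section 6.7 states: "The end of study is the date of the last follow up (videoconference) of the last participant". Section 8.2 counts a serious event as related if it "resulted from administration of any of the research procedures". It requires related and unexpected serious events to be reported within 15 working days of the Chief Investigator learning of them. It sets no collection window and no scheduled enquiry.

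The SAP has no adverse event analysis, and it places the last follow-up at 12 weeks.

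**The concern.** Three features of the schedule make the blank cells at Visits 8 and 9 worth a second look.

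- **The two TMS/MRI sessions are treated unequally.** The first, at Visit 1, is followed by enquiries at six later visits (Visits 2 to 7). The second, at Visit 7, is followed by none at any later visit. The protocol gives no reason.
- **Delayed tDCS effects are asked about only once**, at Visit 7, about a week after the last session. Section 3 describes tDCS as acting on neuronal plasticity and cites an earlier study by the same group in which benefit lasted five weeks. A plan that looks for wanted effects over months could ask about unwanted ones over the same period.
- **The serious-event rule depends on awareness.** Section 6.3 allows unblinding during data collection for a serious event that may be related to the type of stimulation. Data collection runs to Visit 9, but after Visit 7 the team learns of an event only if the participant volunteers it or it otherwise comes to light.

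At stake is what the trial can say about harms after the first follow-up. With no enquiry, an absence of recorded events in that period would not be informative. The efficacy comparison is not affected.

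**Working it through.** The plan states no figure for this gap, so there is none to reproduce. The check reads Appendix B row by row and then counts days.

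**Step 1. Marks in Appendix B**

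| Row | Visits marked |
|---|---|
| Adverse event assessments | 1, 2, 3, 4, 5, 6, 7 |
| tDCS | 2, 3, 4, 5, 6 |
| TMS; brain MRI; vocal tract MRI | 1, 7 |
| BAI | 1, 7, 8, 9 |

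The adverse event row therefore covers every visit at which tDCS, TMS or MRI is given, and no visit after that.

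**Step 2. Days**

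- Last tDCS session (Visit 6): Day 7 (Appendix B).
- Last adverse event assessment (Visit 7): Day 14 or 15 (Appendix B), which is 14 − 7 = 7 or 15 − 7 = 8 days after the last tDCS session.
- Visit 8: Day 7 + 42 = Day 49 (six weeks after Visit 6).
- Visit 9: Day 7 + 84 = Day 91 on the SAP's 12 weeks, or Day 7 + 91 = Day 98 if the protocol's three months is taken as 91 days (assumption).

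**Step 3. Time with no scheduled enquiry**

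Gap = day of Visit 9 − day of last assessment. Share = gap ÷ days from Visit 6 to Visit 9.

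| Follow-up after Visit 6 | Gap | Share |
|---|---|---|
| 84 days | 91 − 15 = 76 to 91 − 14 = 77 days | 76/84 = 90.5% to 77/84 = 91.7% |
| 91 days | 98 − 15 = 83 to 98 − 14 = 84 days | 83/91 = 91.2% to 84/91 = 92.3% |

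**Step 4. Effect of asking at Visits 8 and 9**

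If each enquiry covers the time since the previous one, the whole gap is covered. The longest recall interval would be 91 − 49 = 42 days on the 12-week reading, or 98 − 49 = 49 days on the 91-day reading. The interval from Visit 7 to Visit 8 would be 49 − 15 = 34 to 49 − 14 = 35 days.

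**Step 5. Other routes by which events could be found**

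The tDCS safety screening in section 6.5 applies to Visits 2 to 6. The BAI continues at Visits 8 and 9, but the SAP treats it as an outcome and it concerns anxiety only. Section 8.2 has no end date but starts from awareness. None of these is a general enquiry after Visit 7.

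**The case against.** The case for leaving the schedule alone is reasonable. Assessment takes place at every visit with a physical procedure, and the randomised treatment gets a further assessment 7-8 days after its last session. The two unmarked contacts are remote speech assessments. The protocol describes the risks of tDCS, TMS and MRI after screening as minimal, and the tDCS side effects it lists are sensations under the electrode. No safety outcome is planned. Both arms have the same TMS and MRI, so events from those procedures are not a tDCS-versus-sham effect. All of this stands, and it limits how much the point weighs.

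A reader might also infer more than the documents support:

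- **That the protocol contradicts itself.** It does not. The text for Visits 8 and 9 in section 6.5 matches the blank cells, section 6.7 only defines when the study ends, and section 8.2 sets no enquiry schedule.
- **That nothing after the second TMS/MRI session is assessed.** Visit 7 spans two days and the order within it is not given. The assessment may follow the scans, even on the next day. Only the time after Visit 7 is certainly without enquiry.
- **That a known late harm is being missed, or that a planned long-term safety claim fails.** The documents describe neither.
- **That serious events go unreported after Visit 7.** The duty in section 8.2 continues, and the team still meets participants at Visits 8 and 9.

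What the objection does not answer is that non-serious events after Visit 7 are not solicited at all, and serious ones surface only by chance or by the participant's own report, although two contacts already take place in that period.

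**Conclusion.** The point holds as a gap in collection that is cheap to close. It is not an error or an inconsistency, and its weight is low. Scheduled adverse event enquiry stops at Days 14-15, leaving about 76-77 days (12-week follow-up) or 83-84 days (three months taken as 91 days) to Visit 9. On either reading this is roughly 90-92% of the period after the last tDCS session. Effects of the second TMS/MRI session on the day itself may be captured; delayed ones are not asked about.

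The conclusion rests on two assumptions: that Appendix B as read shows the marks correctly, which the text of section 6.5 supports, and that no enquiry outside the two documents is planned for Visits 8 and 9.

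**What to change.** 1. In Appendix B, mark the adverse event row at Visits 8 and 9, and add the enquiry to the text for those visits in section 6.5. Word it to cover the time since the previous enquiry.
2. State in section 6.5 that the Visit 7 adverse event assessment is done after TMS and MRI.
3. State the collection window (to Visit 9) in section 8.
4. Add to the SAP a descriptive table of adverse events by arm to Visit 9. With 20 participants per arm it should not carry tests. The split by arm is informative for delayed tDCS effects; events attributed to TMS or MRI can also be shown pooled, since both arms have those procedures.

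The cost is two marks, a few lines of text, and a few minutes at each of two contacts that already take place; no visit, procedure or staff is added. The downside is that some unrelated background events will be recorded over the longer window. The same question put to both blinded arms keeps that noise comparable between them.

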Study Title: Investigating Non-invasive brain Stimulation To Enhance fluency in People who stutter

Short title: INSTEP Trial
University of Oxford, Medical Sciences Division
IDREC Ethics Ref: R52173/RE001

Document title: INSTEP trial statistical analysis plan
Date and Version No: 23rd October 2017, version 1.0

Chief Investigator: [name], Department of Experimental Psychology, University of Oxford

Investigators: [name], Department of Experimental Psychology, University of Oxford

[name], Department of Experimental Psychology, University of Oxford

[name], Department of Experimental Psychology, University of Oxford

All the investigators declare that there are no conflicts of interest associated with the proposed study.

INSTEP trial statistical analysis plan

We plan to carry out analyses on the 'intention to treat' sample, i.e. including all participants who complete the study. If any participant has data that are group outliers, we will also complete sensitivity analyses (Thabane et al., 2013) by re-running all analyses excluding the relevant participant(s), to evaluate the robustness of the treatment effect. Speech data in people who stutter tends to significantly deviate from a normal distribution. Transformation of these data is problematic for reporting confidence intervals in interpretable units, therefore we will use change scores (baseline subtracted) in the analyses to overcome this limitation. For consistency, we will use this approach of baseline subtraction and analysis of change scores in analysis of other variables even if they do not suffer from the same skewness as the speech data. Variables that are not normally distributed will be analysed using nonparametric methods.

Primary outcome measure

The primary outcome measure for the trial is the change in stuttering severity, measured using the Stuttering Severity Instrument, version 4 (SSI-4, Riley, 2009). Change from baseline score will be calculated (by subtraction of the baseline) at one week, 6 weeks and 12 weeks following the intervention. Change scores will be entered into a mixed model analysis of variance (ANOVA), with stimulation group (tDCS, sham) as the between subjects factor and speaking task and time point (1 week, 6 weeks, 12 weeks) as the within subjects factor. If a significant interaction between stimulation group and time point is found, separate repeated measures ANOVAs will be performed for each stimulation group or with three planned comparisons between groups at each time point.

Secondary outcome measures

We have three secondary outcome measures:

- i. Change from baseline score in percentage of disfluent syllables, during reading.
- ii. Change from baseline score in percentage of disfluent syllables, during conversation.
- iii. Change in total score on Overall Assessment of a Speaker's Experience of Stuttering (OASES).

Change in percentage of disfluent syllables will be calculated by subtraction of the baseline percentage for reading and conversation separately at one week, 6 weeks and 12 weeks following the intervention. Data will be analysed as described above for the primary outcome measure. Anticipating a significant effect of group in both measures, we will also compare the changes in reading with those in conversation at each time point separately for the tDCS group.

To test for the effects on the OASES measure, we will use a mixed model ANOVA with stimulation group (tDCS, sham) as the between subjects factor and time point (6 weeks, 12 weeks). We will not collect data at the 1-week post-intervention time-point to avoid violating test-retest validity of the scale. If a significant

interaction between stimulation group and time point is found, separate planned comparisons between groups will be performed for each time point.

Other pre-specified measures

We are including the Beck Anxiety Inventory to monitor for any differences in anxiety between the groups, which should be minimized at baseline by the randomization procedure. Any effect of the intervention of stuttering severity may also have consequences for anxiety. We will assess the change in anxiety scores with the same analysis as planned for the primary outcome measure. We will also examine the correlation of the change in anxiety score and the change in (i) stuttering severity (SSI-4), and percentage of disfluent syllables on (ii) reading and (iii) conversation tasks

The Premonitory Awareness in Stuttering Scale (PAiS) tests for anticipation of stuttering events. We have included this as an exploratory measure. We also include subjective ratings of stuttering severity and speech naturalness, and an objective measure of speech naturalness. For each scale (PAiS, subjective severity, subjective naturalness, objective naturalness) change scores will be analysed as described for the primary outcome measure.

In addition, we include exploratory analysis of the effects of tDCS during the intervention period. Effects of tDCS immediately after intervention will be analysed using change in percentage of disfluent syllables (baseline subtracted) measured post-intervention on each day, for both reading and conversation. A mixed model ANOVA will be used with stimulation group (tDCS, sham) as the between subjects factor and time point (day 1 to 5) and task (reading, conversation) as the within-subjects factors. Carry-over of effects following a period including sleep will be analysed using change in percentage of disfluent syllables (baseline subtracted) measured immediately before the intervention, for both reading and conversation. A mixed model ANOVA will be used with stimulation group (tDCS, sham) as the between subjects factor and time point (day 2 to 5) and task (reading, conversation) as the within-subjects factors. The Day 1 time point will be omitted in this analysis, as no intervention will have been performed prior to that measurement.

Finally, in further exploratory analyses, we wish to examine the three submeasures that contribute to the Stuttering Severity Instrument total score. These are: (i) frequency, expressed in percent syllables stuttered and converted to scale scores of 2-18; (ii) duration is the average length of the three longest stuttering events timed to the nearest one tenth of a second and converted to scaled scores of 2-18; and, (iii) physical concomitants for which the four types of physical concomitants are rated on a scale of 0-5 and totaled. We will compare changes from baseline in these variables as described for the analysis of the primary outcome measure.

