6.3. Randomisation, blinding and code-breaking

A 'minimisation' sampling procedure will be used, whereby participants' stuttering severity as measured during screening with the SSI-4 will be used to assign successive participants to true stimulation or sham stimulation, minimising group differences in severity. A member of the Departmental of Experimental Psychology who is not involved with the study will be in charge of communicating to the project team what code they should use.

On the basis of this randomisation, half the participants will receive true tDCS stimulation and the other half will be in a control group that will not receive stimulation (sham tDCS). In sham tDCS the current is applied for a sufficiently brief duration to avoid any change in cortical

excitability (up to 30 seconds) but long enough to produce the transitory sensation on the skin associated with real tDCS. Although the stimulation is different, each participant will receive exactly the same speech training throughout the study.

The study will also be double-blinded, meaning that the researchers, study staff, and participants will not know whether the condition involves real or sham tDCS. The stimulator used in the study has a 'study' mode to allow the operator to be blind to the stimulation condition.

The person in charge of the randomisation procedure will have the capacity to unblind the data for analysis once data collection is complete. Data may be unblinded during the data collection only in the context of a serious adverse event potentially related to the type of stimulation or if a patient withdraws from the study and needs to be replaced.

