Each participant has the right to withdraw from the study at any time. In addition, the Investigator may discontinue a participant from the study at any time if the Investigator considers it necessary for any reason including:

- Ineligibility (either arising during the study or retrospectively having been overlooked at screening)
- Significant protocol deviation
- Significant non-compliance with treatment regimen or study requirements
- Withdrawal of Consent
- Loss to follow up

The reason for withdrawal will be recorded in the Case Report Form. We will replace participants who withdraw from the study, if we are able to do so. With permission, we will use the data of subjects who have withdrawn from the study, if it is usable (e.g. we may use behavioural, neural, or vocal data data that was collected until participant withdrew to evaluate our tertiary objectives). If we do not have the participants' permission to use the data, we will exclude it from our analyses, and all data and information collected from those participants will be securely destroyed.

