9.2. The Number of Participants

We plan to recruit 40 PWS and up to 30 controls. The sample size was determined based on previous cross-sectional studies in stuttering, including our own. A sample size of 20 participants in each group is higher than most previous behavioural and functional imaging studies in PWS. This should ensure sufficient sensitivity to detect differences in behaviour, brain structure and function. It should also allow us to determine the relationship between the experimental variables and other measures such as stuttering severity and duration of stuttering. A sample size of 20 for each group should detect a group difference with an effect size of 0.9 at 80% power and 5% false positive rate. For the tDCS study across 5 days, we will compare two groups of 20 PWS. In our previous study, with sample sizes of 15 in each group, effect sizes of 0.93 and 0.50 were obtained for the reduction in the SSI at 1 week and 6 weeks post intervention.

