9.3. Analysis of Outcome Measures

Only data from participants who have not withdrawn consent will be included in final analyses. If participants drop out, we will attempt to replace their participation.

We will compare measures of speech function based on standardized tests and measures of speech fluency from speech samples. The primary outcome is defined as change in SSI-4 score (baseline subtracted), and the secondary outcomes are change in % disfluency and OASES score.

Differences between sham and tDCS intervention in brain imaging measurements will be evaluated using standardized analysis tools in the FMRIB Software Library. In functional MRI our outcome measures are the intensity and size of activation clusters based on the recorded blood-oxygenation-level-dependent signal (BOLD) that are involved in the tasks we ask participants to complete. Structural image analysis will be employed to measure white matter diffusion and grey matter morphometric differences in areas identified as abnormal in previous studies of stuttering.

Vocal tract imaging data will be analysed using custom tools to calculate the range of positions in tongue blade movement, lip protrusion, and laryngeal lowering during speech production. We predict that spatiotemporal variability in these movements will be greater in PWS compared with controls and reduce in those with measureable improvements in fluency following speech training.

The motor excitability and measures of cortical connectivity obtained using TMS and MEPs will be compared in PWS and Controls and at baseline relative to week 1 to examine for correlates of improved speech fluency in PWS.

We will compare differences in brain and vocal tract imaging data in PWS and controls. Only data from the baseline time point will be used.

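### The SAP's 'intention to treat' set is defined as completers, which conflicts with broader protocol wording and leaves replaced participants and missed follow-ups without a rule

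*SAP*

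**What the plan says.** **SAP, opening paragraph.** The analysis set is given in one sentence: "We plan to carry out analyses on the 'intention to treat' sample, i.e. including all participants who complete the study". Completing is not defined further. The only sensitivity analysis planned there is the exclusion of outliers.

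**SAP, Primary outcome measure.** SSI-4 change at 1, 6 and 12 weeks goes into a mixed between/within ANOVA. Nothing is said about a participant who misses one of the three visits.

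**Protocol section 9.3.** The condition here is consent, not completion: "Only data from participants who have not withdrawn consent will be included in final analyses". It continues: "If participants drop out, we will attempt to replace their participation".

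**Protocol section 6.6, on discontinuation and withdrawal.** Listed reasons for discontinuing a participant include "Significant non-compliance with treatment regimen or study requirements" and loss to follow-up, neither of which requires consent to be withdrawn. On replacement: "We will replace participants who withdraw from the study, if we are able to do so". The section also says withdrawn participants' data will be used if they permit it and the data are usable. As an example it mentions "data that was collected until participant withdrew to evaluate our tertiary objectives".

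**Protocol section 6.3.** Replacement appears again as one of two grounds for unblinding during data collection: "or if a patient withdraws from the study and needs to be replaced".

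**The concern.** Intention to treat means everyone randomised, analysed in the arm to which they were allocated. The words after the SAP's 'i.e.' replace that with people who reached the end. Completion happens after allocation, so it can depend on the arm and on how well the participant is doing. Where it depends on both, the arms being compared are no longer the randomised arms.

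The two documents also give different answers for the same person. A participant lost to follow-up at 6 weeks who never withdrew consent is inside the section 9.3 rule and outside the SAP set. A participant who withdrew but allowed use of existing data is covered by section 6.6 and is again outside the SAP set. A replaced participant is not addressed.

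At stake are a possible bias in the primary contrast, a published label that misdescribes the analysis, and choices about whom to include that could be made after the data are seen. With 20 per arm, each participant is 5% of an arm.

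**Working it through.** **1. The plan's own figure.** Section 9.2 gives 20 per group for an effect size of 0.9, 80% power and 5% error. Taking the test as two-sided: n = 2(1.960 + 0.842)² / 0.9² = 19.4, so 20 per arm. Exact t-test power at 20 per arm is 79.2%. The figure reproduces and contains no dropout allowance (40 = 2 × 20).

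**2. Inputs for the illustration.** From the documents: 20 per arm, and prior effects described as "effect sizes of 0.93 and 0.50 were obtained for the reduction in the SSI at 1 week and 6 weeks post intervention". Assumed, because the documents give no dropout rate: standard normal change scores with higher meaning worse, no true effect, and loss only within the worst-responding third of each arm, at rate p. Expected losses are 20 × p/3: 2.0 at 30%, 2.7 at 40%, 0.7 at 10%.

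**3. Formulas.** The mean of the worst third is 1.091 SD. Removing a fraction p of that third improves the arm mean by 1.091(p/3) / (1 − p/3):
- p = 10%: 0.0364 / 0.9667 = 0.038
- p = 30%: 0.1091 / 0.9000 = 0.121
- p = 40%: 0.1455 / 0.8667 = 0.168

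The shift in the contrast is the sham value minus the tDCS value.

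Replacement has two cases. If replacements face the same selective loss until someone completes, the arm mean is that of completers and the formula is unchanged. If replacements come from the whole population and none is lost, the arm shift is 1.091(p/3).

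**4. Results.** Error is the simulated two-sided t-test rate at 20 per arm.

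| Loss of worst third, sham/tDCS | No replacement: shift, error | Replacements face same loss | Replacements never lost |
|---|---|---|---|
| 30% / 10% | 0.084 SD, 5.7% | 0.084 SD, 5.7% | 0.073 SD, 5.6% |
| 30% / 0% | 0.121 SD, 6.7% | 0.121 SD, 6.7% | 0.109 SD, 6.4% |
| 40% / 10% | 0.130 SD, 6.8% | 0.131 SD, 7.1% | 0.109 SD, 6.4% |
| 40% / 0% | 0.168 SD, 8.0% | 0.168 SD, 8.4% | 0.145 SD, 7.4% |
| 30% / 30% | 0, 5.0% | 0, 5.0% | 0, 5.0% |

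Repeat simulations differ by a few tenths of a point. Across them the ranges for the four unequal rows are about 5.7%-8.1%, 5.7%-8.6% and 5.5%-7.6%.

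**5. Scale.** The standard error at 20 per arm is √(2/20) = 0.316 SD, so the largest shift is 0.168 / 0.316 = 0.53 of it. Against the 0.9 design effect the shift is 0.084/0.9 = 9% to 0.168/0.9 = 19%. Against the prior 0.50 it is 17% to 34%, if 0.50 is a standardised group difference.

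**6. Direction.** Losing poor responders from sham works against tDCS: without replacement, false claims favouring tDCS fall from 2.5% to 0.6%-1.4%. If the pattern reverses, they rise to 4.4%-7.4%.

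**The case against.** A reader might infer that leavers are shut out of the primary analysis by both documents. The protocol does not support that. Section 9.3 read alone keeps someone who is lost to follow-up or discontinued without withdrawing consent. Section 6.6 says withdrawn participants' data will be used with permission and excluded without it, and tertiary objectives appear there only as an example. This part of the objection stands. The defect is the SAP's completer wording set against broader protocol wording, and the need to reconcile them.

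A reader might also infer that the trial result will be biased. The documents give no dropout rate and no sign of unequal loss. Participants and staff are blinded, speech training is the same in both arms, training can take place at home or office, the last two visits are by videoconference, and there is payment for completing. Under no true effect, nothing in the documents explains why poor responders would leave one arm more than the other, and equal selective loss produces no shift. This also stands. It lowers the likelihood of harm but does not make the definition right, and if tDCS does work, response and so loss may differ between arms.

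The third defence is that replacement repairs the damage. It restores numbers. It leaves the bias unchanged if replacements are lost in the same way, and lowers it only modestly if none is lost.

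**Conclusion.** The concern holds in conditional form. The SAP's set is a completer set under an intention-to-treat label. It conflicts with protocol sections 6.6 and 9.3, and no text settles the status of replaced participants or the handling of a missed follow-up.

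Bias arises only if loss depends on both arm and outcome. In the illustrated range it is 0.08-0.17 SD, at most about half a standard error, with two-sided error of about 5.7%-8.1% in place of 5%. These figures rest on assumed loss rates, normal scores and no true effect, and they are not a forecast. With no loss there is no harm.

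This should be corrected before unblinding, because the rule is wrong as written and the correction is cheap. The sample size calculation is not in question here.

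**What to change.** 1. Define the primary set as all randomised participants who stutter, analysed as allocated, using every available post-baseline SSI-4 score that consent allows. Reconcile protocol sections 6.6 and 9.3 and the SAP opening paragraph to say so, and report by arm anyone excluded for lack of permission.
2. Keep replaced participants in the analysis and count their replacements as additional randomised participants.
3. Fit a likelihood-based repeated-measures model to SSI-4 change with group, time and group-by-time, so that partial follow-up is kept. State that it assumes data are missing at random and that it gains nothing from a participant with no post-baseline score.
4. Add a delta-shift sensitivity analysis by arm that includes participants with no post-baseline score, and report where the conclusion changes. Report completers as a sensitivity analysis under that name.

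The cost is SAP and protocol text plus a little more analysis, with no added visits. The speaking-task factor listed for SSI-4 and the SAP's nonparametric rule also need clarifying, but they are separate points that would exist with no dropout at all.
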